3.1 General Study Design

This is a Phase 3, prospective, double-blind, placebo-controlled, multicenter, relapse prevention study in subjects with dementia-related psychosis. Approximately 95 study sites will participate in this study.

The duration of participation for individual study subjects will be up to 47 weeks, consisting of a screening period of up to 5 weeks; an open-label (OL) period of 12 weeks; a double-blind (DB) period of up to 26 weeks; and an approximately 4-week safety follow-up period.

The study discontinuation date is defined as the day on which the Sponsor notifies sites that the study is ending (for example, in the event of a positive interim analysis or after 75 adjudicated relapse events). The study completion date is defined as the day on which the last subject completes the last scheduled assessment (i.e., safety follow-up). A study schematic is provided in [Figure 1](#).

Figure 1 Schematic of Study Design

Screening Period (3-35 Days)

During the screening period, subjects will be assessed for study eligibility and prohibited medications will be discontinued when medically appropriate. Subjects and partner/caregivers will also receive a standardized psychosocial therapy training.

Investigators should not withdraw a subject's prohibited medication for the purpose of enrolling them into the study. Medications should be discontinued only if it is deemed clinically appropriate to do so.

Open-label Period (12 Weeks)

During the open-label period, eligible subjects will begin receiving pimavanserin 34 mg once daily (QD) beginning at Week 0 (open-label Baseline). Subsequent clinic visits will occur at Weeks 2, 4, 8, and 12. Dose adjustments are permitted at scheduled or unscheduled visits until Week 4. After Week 4, the subject's dose will remain fixed at either 34 mg or 20 mg once daily.

To enter the double-blind period, eligible subjects must meet the following response criteria at Weeks 8 and 12:

- Subject experiences a $\geq 30\%$ reduction (improvement) from Week 0 (open-label Baseline) on the Scale for the Assessment of Positive Symptoms – Hallucinations + Delusions (SAPS-H+D) Total Score AND

- Subject has a Clinical Global Impression – Improvement (CGI-I) score of 1 (very much improved) or 2 (much improved), relative to Week 0 (open-label Baseline)

A subject who does not meet response criteria at Weeks 8 and 12 will be withdrawn from study drug and enter the safety follow-up period of the study.

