Pharmacokinetic samples will be collected at Weeks 0, 8, and 12. Pharmacokinetic samples will also be collected, if possible, at any ET visit or the visit immediately following any SAE or following an AE leading to discontinuation.

Double-blind Period (up to 26 Weeks)

Randomization will occur at the double-blind Baseline visit (Week 12). Subjects will be randomly assigned 1:1 to continue their pimavanserin dose (34 mg or 20 mg) or matching placebo.

The protocol-defined relapse criteria for dementia-related psychosis are designed to identify subjects with an impending relapse or relapse of psychosis:

- Subject experiences a $\geq 30\%$ increase (worsening) from Week 12 (double-blind Baseline) on the SAPS-H+D Total Score AND has a CGI-I score of 6 (much worse) or 7 (very much worse), relative to the double-blind Baseline; OR
- Subject is treated with an antipsychotic (other than pimavanserin) for dementia-related delusions and/or hallucinations; OR
- Subject stops study drug or withdraws from study for lack of efficacy, (as reported by the subject or study partner/caregiver) or the Investigator discontinues study drug due to lack of efficacy; OR
- Subject is hospitalized for worsening dementia-related psychosis

Relapse criteria will be assessed weekly for the first 2 weeks after randomization (Weeks 13 and 14), every 2 weeks until Week 26, and every 4 weeks through Week 38. Relapse criteria may also be evaluated at unscheduled visits. Any subject who meets any of the relapse criteria after randomization will be withdrawn from study drug and enter the safety follow-up period of the study.

All subjects who discontinue the study between randomization and Week 38 should complete an ET visit, if possible. The Independent Adjudication Committee (IAC) will adjudicate early termination and relapse events that occurred before the study discontinuation date. Early termination and relapse events that occur in the double-blind period after the study discontinuation date will not be adjudicated.

An interim and final analysis will be planned after 38 and 75 adjudicated relapse events have occurred, respectively. The study may be terminated early if the interim analysis results establish the efficacy and safety of pimavanserin for the treatment of hallucinations and delusions associated with dementia-related psychosis.

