3.4 Determination of Sample Size

This study will enroll approximately 356 subjects in order to randomize approximately 178 subjects with dementia-related psychosis who meet response criteria at Weeks 8 and 12 of the open-label period.

The sample size calculation was based on the following assumptions: a placebo relapse event rate of 60% over 26 weeks; a pimavanserin relapse event rate of 35% over 26 weeks (hazard ratio = 0.47); a dropout rate of 25% over 26 weeks; an overall two-sided alpha level of 0.05; use of a one-sided (0.025) O’Brien-Fleming stopping boundary to adjust for a single interim

analysis that will be performed when one half of the total planned number of post-randomization relapse events have occurred; and a power of 90%. The total number of post-randomization relapse events required at the final analysis is 75 and the calculated sample size is 89 in each of the two treatment groups (giving a total estimate of 178 subjects). Study enrollment will be closed when approximately 178 subjects have been randomized in the double-blind period or when 75 adjudicated post-randomization relapse events have occurred. In the event that the randomization rate is lower than anticipated and/or the relapse event rate is lower than anticipated, the number enrolled and randomized may be increased up to a maximum of 400 randomized subjects in order to observe 75 post-randomization relapse events. If fewer than 75 post-randomization relapse events have been observed after 400 randomized subjects have completed the study or terminated early, the study will end. An interim efficacy analysis will be performed, and the study may be terminated early if the interim analysis results meet prespecified stopping criteria.(see [Section 16](#))

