11 EXTENT OF EXPOSURE AND TREATMENT COMPLIANCE

11.1 Exposure to Study Drug

The duration of exposure during the open-label period and the double-blind period for a given subject will be calculated separately. Duration of exposure to study drug will be summarized descriptively as both continuous and categorical variables for the open-label period and the double-blind period.

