11.1.2 Analysis for the Double-blind Period

Duration of exposure during the double-blind period for a given subject is calculated as follows:

$$\text{DB Duration of exposure} = \text{last DB dose date} - \text{first DB dose date} + 1$$

For the categorical presentation of duration of exposure during the double-blind period, the number and percentage of subjects in each of the following categories will be displayed: <1 week, 1 to <2 weeks, 2 to <4 weeks, 4 to <8 weeks, 8 to <12 weeks, 12 to <18 weeks, 18 to <26 weeks, and ≥ 26 weeks. Summaries of duration of exposure will be provided for the Double-blind Safety Analysis Set. In addition, Kaplan-Meier curves of duration of exposure will be provided.

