14.1 Adverse Events

All Adverse events (AEs) will be coded using MedDRA version 20.0 or newer.

An AE (classified by preferred term) will be considered a treatment emergent AE (TEAE) if the onset date was on or after the date of first dose of open-label pimavanserin and up to 30 days past the last dose of study drug. AEs reported on Day 1 based on open-label Baseline (pre-dose) findings (e.g. clinically significantly abnormal vital signs, laboratory test results, or electrocardiogram parameters) will not be considered as TEAEs.

Each TEAE will be assigned to either the open-label or double-blind period based on the onset date. For randomized subjects, if the onset date was on or after the date of first dose of double-blind study drug, the TEAE will be assigned to the double-blind period. All other TEAE will be assigned to the open label period.

The event counts and the number and percentage of subjects reporting TEAEs will be tabulated by SOC and preferred term; and, by SOC, preferred term, and maximum severity. If more than 1 AE occurs with the same preferred term for the same subject, the subject will be counted only once for that preferred term using the most severe occurrence for the

summarization by severity. In addition, the event counts and the number and percentage of subjects with TEAEs classified by the Investigators as related to the study drug, with most frequently reported TEAEs (preferred terms reported by $\geq 5\%$ of subjects overall for the open-label period and $\geq 5\%$ of subjects in either treatment group for the double-blind treatment period), with treatment emergent serious AEs, with fatal AEs (i.e. events that cause death), and with TEAEs leading to discontinuation of study drug will be summarized by SOC and preferred term. The display in these tables will be sorted alphabetically by SOC and then by descending subject frequency for the preferred terms using combined counts from both groups within each SOC. The event counts and the number and percentage of subjects with any TEAEs will also be tabulated by preferred term without SOCs. This table will be sorted by descending subject frequency using combined counts from all subjects.

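### SAP 14.1 compares double-blind adverse events between arms only by counts and crude percentages, although relapse is expected to shorten time at risk on placebo; a Kaplan-Meier time-to-first-event summary should be added

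*SAP*

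**What the plan says.** SAP Section 14 presents double-blind safety data by treatment group. For adverse events, Section 14.1 says: "The event counts and the number and percentage of subjects reporting TEAEs will be tabulated by SOC and preferred term". The same form (event counts, number and percentage of subjects) applies to related, serious and fatal events and to those leading to discontinuation. An event is treatment-emergent if it starts on or after the first open-label dose and "up to 30 days past the last dose of study drug". Section 14.1 has no person-time denominator and no time-to-first-event estimate. Protocol 9.5.4 also promises descriptive summaries only.

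Relapse ends treatment in both arms (SAP 3.1): "Any subject who meets any of the relapse criteria after randomization will be withdrawn from study drug". The sample size in SAP 3.4 assumes "a placebo relapse event rate of 60% over 26 weeks; a pimavanserin relapse event rate of 35% over 26 weeks" and "a dropout rate of 25% over 26 weeks". Follow-up may also be cut short by the sponsor, "in the event of a positive interim analysis or after 75 adjudicated relapse events" (SAP 3.1).

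Exposure is covered in SAP 11.1: "Duration of exposure to study drug will be summarized descriptively as both continuous and categorical variables". Section 11.1.2 adds duration categories and Kaplan-Meier curves, with exposure running from first to last double-blind dose. Nothing links exposure to the adverse event tables. SAP Section 1 says that table specifications are in a separate document, which was not available.

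**The concern.** If the drug prevents relapse as planned, pimavanserin subjects stay on study longer and have more time in which to report an event. A crude percentage then mixes the event hazard with the time at risk and cannot separate the two. The larger the efficacy effect, the less comparable the two columns become.

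This matters because the safety objective (Protocol 2.4) is a comparison with placebo, and Protocol 1.3.1 cites a boxed warning on death with antipsychotics in elderly patients with dementia-related psychosis. Serious and fatal events are where readers will compare the arms most closely. A small excess on pimavanserin could be only longer observation, and apparent equality could hide a difference in hazard. The issue is how descriptive tables are read; no type I error is involved.

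**Working it through.** **Inputs** (SAP 3.4, 3.1, 14.1): 26-week relapse 60% and 35%; dropout 25%, taken as equal in both arms; 89 per arm; 26-week double-blind period; TEAE window of 30 days = 4.29 weeks.

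**The plan's own figures reproduce.** The 26-week hazards are -ln(0.40) = 0.916, -ln(0.65) = 0.431 and, for dropout, -ln(0.75) = 0.288. HR = 0.431/0.916 = 0.47, as stated. With dropout as a competing exit, the probability of an observed relapse is (0.916/1.204) x (1 - 0.40 x 0.75) = 0.533 on placebo and (0.431/0.7185) x (1 - 0.65 x 0.75) = 0.307 on pimavanserin. The mean is 0.420, and 75/0.420 = 178.6 against the stated 178. The same assumptions can therefore be used for exposure.

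**Time at risk.** With exit rate k per week, mean time on drug is (1 - exp(-26k))/k.
- Placebo: 26 x (1 - 0.300)/1.204 = 15.12 weeks.
- Pimavanserin: 26 x (1 - 0.4875)/0.7185 = 18.55 weeks; ratio 1.227.
- With the 30-day window: 19.40 and 22.83 weeks; ratio 1.177. The window is 22% and 19% of time at risk.

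**Crude percentage at equal, constant hazard.** Let h = -ln(1 - risk)/26 and w = 4.29. Then

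crude = 1 - exp(-hw) x [ k/(k+h) x (1 - exp(-26(k+h))) + exp(-26(k+h)) ].

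At 10% risk, h = 0.00405 and exp(-hw) = 0.983:
- Placebo: 1 - 0.983 x (0.9195 x 0.730 + 0.270) = 7.5%.
- Pimavanserin: 1 - 0.983 x (0.872 x 0.561 + 0.439) = 8.8%.

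| 26-week risk | Placebo | Pimavanserin | Ratio |
|---|---|---|---|
| rare (limit) | | | 1.18 |
| 10% | 7.5% | 8.8% | 1.17 |
| 40% | 30.5% | 35.1% | 1.15 |
| 90% | 75.2% | 81.2% | 1.08 |

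**Sampling error, 89 per arm.** At 10% risk the gap is 1.3 points, with SE sqrt[(0.075 x 0.925 + 0.088 x 0.912)/89] = 4.1 points. At 40% it is 4.6 points with SE 7.0.

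**Other cases, 10% risk.**
- Relapse 60%/45%: 1.11; 50%/35%: 1.09; equal relapse: 1.00.
- Sponsor stop at 38 events: 1.09-1.15. Accrual is not in the documents; uniform accrual of 178 subjects over 26-130 weeks is assumed.

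**Which added measure behaves well?** The table gives ratios, pimavanserin to placebo, at 10% risk with equal true on-drug hazards. The timing and post-relapse patterns are assumptions. Rates are first events per person-time.

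| Scenario | Crude % | On-treatment rate | TEAE-window rate | On-treatment Kaplan-Meier, Week 26 |
|---|---|---|---|---|
| Constant hazard | 1.17 | 1.00 | 1.00 | 1.00 |
| Risk only in weeks 0-4 | 1.00 | 0.84 | 0.85 | 1.00 |
| Risk only in weeks 0-8 | 1.015 | 0.88 | 0.87 | 1.00 |
| Risk only in weeks 0-13 | 1.05 | 0.92 | 0.90 | 1.00 |
| Hazard 2 times higher after relapse | 1.11 | 1.00 | 0.95 | 1.00 |
| Hazard 3 times higher after relapse | 1.06 | 1.00 | 0.90 | 1.00 |
| Hazard 5 times higher after relapse | 0.99 | 1.00 | 0.84 | 1.00 |

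At 4 times the crude ratio is 1.02. The window rate falls below 1 because treatment ends in relapse in 53% on placebo and 31% on pimavanserin, so the post-relapse tail falls more often on placebo.

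**Can the planned tables be combined instead?** Dividing event counts by n x mean exposure puts window events over on-drug time. At equal constant hazards this inflates the rate by 19.40/15.12 = 1.284 on placebo and 22.83/18.55 = 1.231 on pimavanserin, a ratio of 0.96. Counts also include repeat events.

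**The case against.** The strongest case against is that this is a reporting preference. The protocol promises descriptive safety summaries and the SAP delivers them. Exposure will be visible by arm in statistics, categories and Kaplan-Meier curves, event counts stand beside the percentages, and the listings give each event's study day. A reader can see that exposure differs and can approximate a rate that errs by only 4% in the base case. For one term the shift is about a third of a standard error at 10% risk (1.3/4.1) and two thirds at 40% (4.6/7.0). The unseen table specifications may already contain an exposure-adjusted display.

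Much of this stands. It keeps the point minor and limits it to the SAP text. It does not remove it: first-event estimates cannot be read from the planned tables, and the size, possibly the direction, of the distortion differs by term, so no single mental correction works.

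A second objection is aimed at the usual remedy, and it is right. Events per 100 patient-years assume a constant hazard. For early-onset events they read 0.84-0.92 with no true difference, where the crude percentage is nearly unbiased. A rate over the TEAE window can also mislead for deaths: with a hazard 3 or 5 times higher after relapse it reads 0.90 or 0.84, against 1.06 or 0.99 for the crude percentage. Person-time rates should therefore not be the main addition.

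**Conclusion.** The point holds as a low-cost improvement to consider. As written, SAP 14.1 gives a between-arm comparison that is confounded by time at risk if relapse differs as planned. The relative excess on pimavanserin is at most about 15-18% for events with a 26-week risk up to 40%, and 8% at 90% risk. That ceiling rests on 60%/35% relapse, 25% dropout equal in both arms, exponential exits, full 26-week follow-up and an adverse event hazard that is constant and equal between arms through the 30-day window. It falls to 0-5% for events confined to the first 4-13 weeks, to zero at equal relapse, and to about zero or slightly below if the hazard is 4-5 times higher after relapse.

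A reader might infer that every adverse event row will overstate pimavanserin by 15-18%, or that the plan conceals exposure. The documents support neither. The first needs all of the assumptions above at once, and the second is contradicted by SAP 11.1.2. Nor can it be said that no exposure-adjusted table is planned, because the table specifications were not available.

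**What to change.** In SAP 14.1, keep crude n (%) and event counts. For any TEAE, serious TEAEs and deaths, add by arm:

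- **Main addition:** a Kaplan-Meier estimate of time from first double-blind dose to first event, censored at last dose or data cutoff, with the difference at Week 26 and its 95% CI. If cumulative incidence is preferred, only death should compete. Counting the end of treatment as a competing event would bring back the crude on-treatment percentage, whose ratio is 1.22 at 10% risk.
- **Beside it:** the same estimate run to the end of the 30-day TEAE window, so that events soon after stopping are kept. For deaths, report both and do not lead with the window version.
- **Optional support:** first events per 100 patient-years, with a note that for early-onset events they read about 0.84-0.92, favouring pimavanserin, when there is no true difference.

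Label all of this descriptive and fix the censoring rules before unblinding.

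Cost: a short SAP paragraph and a few tables from data already collected. Intervals will be wide at 89 per arm, and censoring at relapse or dropout must be assumed non-informative for adverse events, which the SAP should say.

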3.4 Double-blind Period (up to 26 Weeks)

Randomization will occur at the double-blind Baseline visit (Week 12). Subjects will be randomly assigned 1:1 to continue their pimavanserin dose (34 mg or 20 mg) or matching placebo.

The protocol-defined relapse criteria for dementia-related psychosis are designed to identify subjects with an impending relapse or relapse of psychosis:

- Subject experiences a $\geq 30\%$ increase (worsening) from Week 12 (double-blind Baseline) on the SAPS-H+D Total Score AND has a CGI-I score of 6 (much worse) or 7 (very much worse), relative to the double-blind Baseline¹; OR
- Subject is treated with an antipsychotic (other than pimavanserin) for dementia-related delusions and/or hallucinations; OR
- Subject stops study drug or withdraws from study for lack of efficacy, (as reported by the subject or study partner/caregiver) or the Investigator discontinues study drug due to lack of efficacy; OR
- Subject is hospitalized for worsening dementia-related psychosis

Relapse criteria will be assessed weekly for the first 2 weeks after randomization (Weeks 13 and 14), every 2 weeks until Week 26, and every 4 weeks through Week 38. Relapse criteria may also be evaluated at unscheduled visits. Any subject who meets any of the relapse criteria after randomization will be withdrawn from study drug and enter the safety follow-up period of the study.

All subjects who discontinue the study between randomization and Week 38 should complete an ET visit, if possible, and an independent adjudication committee (IAC) will review those cases that occurred before the study discontinuation date to determine if protocol-defined relapse criteria were met.

Pharmacokinetic samples will be collected at Weeks 13, 22, and 38/EOT. Pharmacokinetic samples will also be collected, if possible, at any ET visit or the visit immediately following any SAE or following an AE leading to discontinuation.

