7 ADVERSE EVENTS

7.1 Specification of Safety Parameters

7.1.1 Definition of Adverse Event

An AE is defined as “any untoward medical occurrence associated with the use of a drug in humans, whether or not considered drug related” ([US FDA 2012b](#)).

An AE can therefore be any unfavorable and unintended sign (e.g., an abnormal laboratory finding), symptom, or disease temporally associated with the use of a drug, without any judgment about causality or seriousness. An AE can arise from any use of the drug (e.g., off-label use, use in combination with another drug) and from any route of administration, formulation, or dose, including an overdose.

A suspected adverse reaction is any AE for which there is a reasonable possibility that the drug caused the AE.

AEs do not include the following:

- Stable or intermittent chronic conditions (such as myopia requiring eyeglasses) that are present prior to Baseline and do not worsen during the study
- Medical or surgical procedures (e.g., surgery, endoscopy, tooth extraction, transfusion). The condition that leads to the procedure is an AE if not present at the open-label Baseline.
- Overdose of either study drug (see [Section 7.4.4](#)) or concomitant medication without any signs or symptoms unless the subject is hospitalized for observation
- Hospitalization for elective surgery planned prior to study (situation where an untoward medical occurrence has not occurred)
- Pregnancy will not be considered an AE, but if it occurs, it will be reported on a pregnancy form

Adverse events will be recorded from the time informed consent is obtained through 30 days after the last dose of study drug.

All AEs must be either resolved or stable at end of study. If ongoing at the end of the study the subject should be referred for appropriate treatment.

Serious AEs occurring after the safety follow-up period should be reported if in the judgment of the Investigator, there is “a reasonable possibility” that the event may have been caused by the study drug.

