7.1.2 Definition of Serious Adverse Event

In addition to the severity rating, each AE will be classified by the Investigator as “serious” or “not serious.” The seriousness of an event will be defined according to the applicable regulations and generally refers to the outcome of an event. An SAE is one that meets one or more of the following:

- Is fatal
- Is immediately life threatening
- Results in disability or permanent damage
- Requires hospitalization
- Prolongs existing hospitalization
- Is a congenital anomaly or birth defect (in an offspring)
- Is medically significant

Definition of Life Threatening

A life threatening event places the subject at immediate risk of death from the event as it occurred. This does not include an AE that might have had an outcome of death had it occurred in a more severe form.

Definition of Hospitalization

Hospitalization is defined as a full admission to the hospital for diagnosis and treatment. This includes prolongation of an existing inpatient hospitalization.

Examples of visits to a hospital facility that do not meet the serious criteria for hospitalization include:

- Emergency room visits (that do not result in a full hospital admission)
- Outpatient surgery
- Preplanned or elective procedures
- Protocol procedures
- Social hospitalization, defined as admission to the hospital as a result of inadequate family support or care at the subject's primary residence

Definition of Disability or Permanent Damage

Disability is defined as a persistent or significant incapacity or substantial disruption of the ability to conduct normal life functions.

Definition of Medically Significant

Important medical events (medically significant events) that may not result in death, be life threatening, or require hospitalization may be considered to be an SAE when, based upon appropriate medical judgment, they may jeopardize the subject or may require medical or surgical intervention to prevent one of the outcomes listed in this definition. Examples of such events are intensive treatment in an emergency room or at home for allergic bronchospasm, blood dyscrasias, or convulsions that do not result in hospitalization or development of drug dependency or drug abuse.

An SAE may also include any other event that the Investigator or Medical Monitor judges to be serious or that suggests a significant hazard, contraindication, side effect, or precaution.

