7.4 Reporting Procedures

7.4.1 Adverse Event Reporting

The Investigator must record all observed AEs and all reported AEs. At each visit, the Investigator should ask the subject a nonspecific question (e.g., “Have you noticed anything different since your last visit?”) to assess whether any AEs have been experienced since the last report or visit.

Note that any use of medication (and specifically any newly prescribed medication) during the course of a study may indicate the occurrence of an AE that may need to be recorded on both the AE and the concomitant medication page.

All AEs will be coded by Data Management using MedDRA.

All AEs, serious and not serious, will be recorded on the AE eCRF page using appropriate medical terminology. Severity and relationship to study drug will be assessed by the Investigator as described above.

When possible, clinical AEs should be described by diagnosis and not by symptoms (e.g., “cold” or “seasonal allergies” instead of “runny nose”).

All AEs, *whether or not related to the study drug*, must be fully and completely documented on the AE eCRF and in the subject’s notes.

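### If sites record psychosis relapses as adverse events, SAP 14.1 carries the efficacy difference into the subject-level safety totals, and no summary without relapse records is planned

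*SAP*

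**What the plan says.** Protocol 7.1.1 defines an AE as "any untoward medical occurrence associated with the use of a drug in humans, whether or not considered drug related". Its list of exceptions spares stable or intermittent chronic conditions only if they are ones "that are present prior to Baseline and do not worsen during the study". The list does not mention relapse, worsening psychosis or lack of efficacy.

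Protocol 7.1.2 includes "Requires hospitalization" among the SAE criteria. It names kinds of hospital visit that do not count, such as social or preplanned admissions, and an admission for relapse is not one of them. Protocol 7.4.1 adds that newly prescribed medication "may indicate the occurrence of an AE that may need to be recorded".

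In Protocol 3.4, the first relapse criterion is a 30% or greater "increase (worsening) from Week 12 (double-blind Baseline) on the SAPS-H+D Total Score" together with a CGI-I of 6 or 7. The other criteria are antipsychotic treatment for the psychosis, stopping for lack of efficacy, and "Subject is hospitalized for worsening dementia-related psychosis". The same section continues: "Any subject who meets any of the relapse criteria after randomization will be withdrawn from study drug".

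SAP 14.1 tabulates all TEAEs and treatment-emergent serious AEs by SOC and preferred term, and says that subjects "with TEAEs leading to discontinuation of study drug will be summarized by SOC and preferred term". It has no flag, exclusion or separate category for records that describe the relapse itself. Protocol 9.5.4 says only that AEs may be put into categories of special interest.

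**The concern.** The primary efficacy event can also be an adverse event. A relapse is a deterioration of the condition under study. A relapse that leads to admission meets an SAE criterion. A new antipsychotic is the kind of new prescription that Protocol 7.4.1 asks sites to consider. Because every relapse stops study drug, a relapse entered on the AE page would naturally become a TEAE leading to discontinuation.

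Protocol 2.4 and 2.4.1 make comparison with placebo on TEAEs, SAEs and withdrawals due to AEs part of the safety objective. If the drug prevents relapse and relapses sit in those counts, placebo looks less well tolerated for a reason that is efficacy. A real excess of other events on pimavanserin could then be offset in the totals. If sites differ in what they record, the size of the offset is unknown. The DSMB, which reviews AE and SAE data under SAP 17, would see the same mixture.

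**Working it through.** **1. Reproduce the plan's figures.** Inputs from Protocol 9.3: relapse 60% on placebo and 35% on pimavanserin over 26 weeks, dropout 25%, two-sided alpha 0.05, power 90%, 75 events, 89 per arm.

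- Hazards per 26 weeks: placebo −ln(0.40) = 0.9163; pimavanserin −ln(0.65) = 0.4308; dropout −ln(0.75) = 0.2877.
- Hazard ratio: 0.4308 / 0.9163 = 0.470, as stated.
- Schoenfeld's formula gives 74 events for a fixed design. With 75 events and the final level of 0.0479, power is 90.1%.
- Observed relapse, with constant hazards and dropout as a competing risk, is λ/(λ+δ) × [1 − exp(−(λ+δ))].
  - Placebo: 0.9163/1.2040 × (1 − 0.30) = 53.3%.
  - Pimavanserin: 0.4308/0.7185 × (1 − 0.4875) = 30.7%.
- The mean is 42.0%, and 75/0.420 = 178.6 subjects against 178 planned. In 89 per arm, about 47 and 27 relapse.

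The gap between arms is 22.5 points.

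**2. TEAEs leading to discontinuation.** Let f be the share of relapses recorded as AEs. The documents do not give it, so it is varied. Relapse and non-relapse discontinuations are taken as additive, since a subject stops study drug once. For illustration, assume true non-relapse AE discontinuation of 10% on pimavanserin and 5% on placebo. The tabulated rates are then 10 + f × 30.7 and 5 + f × 53.3.

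| f | Gap added against placebo (points) | Tabulated, pimavanserin vs placebo | Ratio |
|---|---|---|---|
| 0% | 0 | 10.0% vs 5.0% | 2.00 |
| 10% | 2.3 | 13.1% vs 10.3% | 1.27 |
| 25% | 5.6 | 17.7% vs 18.3% | 0.97 |
| 50% | 11.3 | 25.4% vs 31.6% | 0.80 |
| 100% | 22.5 | 40.7% vs 58.3% | 0.70 |

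A true excess of x points is cancelled at f = x/22.5: 13% for 3 points, 22% for 5 points, 44% for 10 points.

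**3. Serious TEAEs.** Let h be the share of relapses that are hospitalized, again not given. The shift is at most h × 22.5 points, because a subject with another SAE is already counted: 1.1 points at h = 5% (2.4 vs 1.4 subjects of 89) and 6.8 at h = 30% (14.2 vs 8.2). For scale only, the Phase 2 study in Protocol 1.3.2 reported SAEs in 16.7% on pimavanserin and 11.0% on placebo, a difference of 5.7 points. A difference of that size would be offset at h = 5.7/22.5, about 25%. That was a 12-week nursing-home study of a different design.

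**4. Any TEAE.** This total is not additive, because a relapser with another TEAE is already counted. Under independence the rate is 1 − (1 − base) × (1 − f × relapse). With assumed base rates of 50% on pimavanserin and 40% on placebo, the tabulated rates are 53.8% vs 48.0% at f = 25%, 57.7% vs 56.0% at f = 50%, and 65.4% vs 72.0% at f = 100%.

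**The case against.** A reader might infer that the definitions turn every relapse into an AE, so that the plan is bound to report efficacy as safety and conceal a tolerability problem. The documents do not support that.

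- **Recording is not prescribed.** No text tells sites to enter a relapse as an AE. Protocol 3.3 requires at least a 30% fall in SAPS-H+D from Week 0 before randomization, while relapse is measured from Week 12. At the minimum thresholds, a relapse stands at 0.70 × 1.30 = 0.91 of the open-label score. The exception in Protocol 7.1.1 does not say which Baseline it means. A site could therefore fairly read such a relapse as a chronic condition that has not worsened. The lack-of-efficacy criterion needs no measured worsening at all. The medication note in Protocol 7.4.1 is general and does not name antipsychotics.
- **Disposition keeps the two apart.** Protocol 4.4 and SAP 6.2 and 13.2 list relapse and adverse event as different reasons for discontinuation. This partly protects the endpoint of withdrawals due to AEs.
- **Rows remain readable.** The SAP 14.1 tables are by SOC and preferred term, so an excess of falls or urinary infections keeps its own row. Subject listings are planned, and the safety analysis is descriptive.
- **Other documents exist.** Table specifications (SAP 1) and SAE reporting details (Protocol 7.4.2) are held elsewhere and may say more.

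All of this stands, and it makes the point conditional without removing it. The disposition tables do not govern the AE and SAE tables, and no rule reconciles the two. Rows do not help with subject-level totals, the psychiatric SOC, or terms that overlap with relapse, such as agitation, which Protocol 1.3.2 reports as more frequent on pimavanserin in Phase 2. Listings allow sorting only after the fact. The freedom left to sites means that the totals could not be interpreted without a flag.

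**Conclusion.** The point holds in conditional form. The AE wording can cover a relapse, the SAE wording clearly covers a hospitalized one, and SAP 14.1 plans no summary without relapse records. To the extent that relapses are recorded as AEs, the totals for any TEAE, serious TEAEs and TEAEs leading to discontinuation, together with the psychiatric SOC, move in favour of pimavanserin. Other preferred-term rows do not.

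The relapse rates rest on the plan's assumptions and constant hazards. The share of relapses recorded or hospitalized is assumed throughout, so the 23-point figure for AE discontinuations is an upper bound and not a forecast. The risk does not need that extreme: under additivity, about 22% recorded is enough to cancel a true 5-point excess. The plausible SAE shift is about 1 to 7 points if 5% to 30% of relapses are hospitalized. The primary efficacy analysis is not affected.

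**What to change.** In SAP 14.1, before unblinding, prespecify a list of preferred terms that describe relapse (hallucination, delusion and psychosis terms), drawn up blind to treatment. Mark a double-blind AE record when its term is on the list and its timing ties it to the investigator-identified or adjudicated relapse date. Present any TEAE, serious TEAE and TEAE leading to discontinuation by arm, both including and excluding the marked records. SAE reporting to the sponsor stays unchanged.

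The cost is one blinded term list and three repeated tables. The downside is some judgement in marking records, which is limited by doing it blind and by showing both versions. The two versions are useful whichever way sites recorded relapses: if few were recorded, the tables will agree.
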